6.2. According-to-protocol cohort for analysis of safety

The ATP cohort for analysis of safety will include all vaccinated and eligible subjects:

- Who did not have a GeneXpert-positive sputum at screening
- Who have received at least one dose of study vaccine according to their random assignment.
- For whom study vaccines have been administered according to protocol (administration site and route).
- Who have not received a vaccine that may lead to elimination from an ATP analysis.
- Who have received a vaccine (effective treatment number) without a temperature deviation.
- Who have received a vaccine (effective treatment number) before its expiration date.
- For whom the randomisation code has not been broken.
- Without randomisation failure.

For the analysis of solicited AEs and clinical laboratory observations, the ATP cohort for safety will include subjects from the safety and immunogenicity sub-cohort only.

6.3. According-to-protocol cohort for analysis of immunogenicity

The ATP cohort for immunogenicity will include all subjects from the safety and immunogenicity sub-cohort and from the ATP cohort for safety:

- Who are without selected protocol violation linked to the inclusion/exclusion criteria (whose age is not in 18-50 years, who are HIV+ at screening, who have negative Interferon-Gamma Release Assay (IGRA) at screening, or, who have a GeneXpert-positive sputum at screening) (note if rescreening, or double result at screening, use the last one for each of the considered test)

- Who received two vaccinations according to protocol procedures within specified intervals.
- Who complied with blood sampling schedules.
- Who did not present with TB disease, according to any definition, during the study.
- Who did not get HIV-infected during the study.
- Who had biochemistry and haematology values within normal range before any vaccination (exclude only if all values were out of range).
- For whom post vaccination blood samples are available.
- Who did not receive a vaccine/medication that may lead to elimination of an ATP analysis.
- Who did not present with a medical condition that may lead to elimination of an ATP analysis.
- Who signed the informed consent for the safety and immune sub-cohort.
- For whom the randomization code has not been broken.
- Without randomisation failure.

6.4. According-to-protocol cohort for analysis of efficacy

The ATP cohort for efficacy will include all subjects from the ATP cohort for safety:

- Who received 2 doses of M72/AS01_E or placebo according to their random assignment.
- Received both vaccinations according to protocol procedures (correct site and route) within specified intervals.
- Who entered the evaluation period for efficacy starting one month post-dose 2, i.e. who have entered into the efficacy surveillance period.
- Who did not present with TB disease, according to any case definition, during the vaccination period (day of first vaccination up to 1 month post-dose 2).
- Who did not receive a vaccine/medication that the CRDL assesses as justifying elimination from the ATP analysis.
- Who did not present with a medical condition that the CRDL assesses as justifying elimination from the ATP analysis.
- Who have received a vaccine (effective treatment number) without a temperature deviation.
- Who have received a vaccine (effective treatment number) before its expiration date.
- For whom the randomization code has not been broken.
- Without randomisation failure.

7. STUDY DESIGN AND PROCEDURES

Refer to latest version of the protocol.

8. GENERAL STUDY ASPECTS

Refer to latest version of the protocol.

9. PLANNING OF ACTIVITIES

Timeframe	Activities
FSFV	August 2014
During the study	Several analyses for IDMC, especially before last subject last dose 2
Before datalock point	Clean ATP efficacy

Before datalock point, a first check of the elimination codes to be assigned to subjects for the ATP cohort for efficacy (and safety) will be organised (draft Pre-Analysis Meeting PAM). After all subjects have completed 24 months of follow-up, the final PAM for the primary analysis will be organised.

Timeframe	Activities
Every 2 months	Case review
2-3 times/year	IDMC
When 18 primary TB cases are accrued	Weekly case review
From 21 primary TB cases are accrued until all subjects complete their M24 visit	Continuous review of the entire database by the data management and preparation of the triggered primary analysis
When all subjects have completed 24 months of follow-up	All analyses will be performed by an external statistician: efficacy analysis + IDMC + Analysis of safety with masking of single events
Month 36 (study completion)	All analyses

10. ANALYSIS OF EFFICACY

10.1. Time-to-event variables

The time-to-event variable will be the time elapsed from the time origin to the end date (end of the follow-up for that subject). In order to avoid mathematical problems which would occur in case the time variable equals zero when an event occurred the same day as the time origin, the first day counts as 1 thus the time to event is calculated as (end date – date of time origin + 1).

The time origin for the start of follow-up in the TVC for efficacy will be the date of the Day 0 visit (date of the first dose of study vaccine) and all cases occurring after Day 0 will be included in the analysis.

The time origin for the start of the follow-up in the ATP cohort for efficacy will be the date of 30 days post dose 2 and all cases occurring on or after 30 days post dose 2 will be included in the analysis.

Table 3 Time origin

Analysis	Cohort	Risk Period	Start
Triggered Primary Analysis	ATP	[30 days post dose 2 – time when all subjects have completed 24 months of follow-up]	30 days post dose 2 of M72/AS01 _E or placebo
Triggered Primary Analysis	TVC	[day of first vaccination-time when all subjects have completed 24 months of follow-up]	Day of first vaccination of M72/AS01 _E or placebo vaccine
End of study analysis	ATP	[30 days post dose 2 – Month 36]	30 days post dose 2 of M72/AS01 _E or placebo
End of study analysis	TVC	[day of first vaccination-Month 36]	Day of first vaccination of M72/AS01 _E or placebo vaccine

ATP = ATP cohort for efficacy

TVC = Total Vaccinated Cohort

10.2. Triggered Primary Analysis when all subjects have completed 24 months of follow-up

As explained in Section 9, the date of the last month 24 visit will be monitored. This calendar date will be defined as the database lock.

Cleaning of the required data will be performed as extensively as possible before that calendar date, but finalization of cleaning will occur during several weeks following this calendar date. Therefore the database freeze will only occur after end of cleaning of the data which will then be analysed. Therefore, the table below describes what will happen to data collected before the database lock, and between the database lock and the freezing.

A period of 6 weeks is planned between database lock and database freeze (DBF) in order to obtain laboratory confirmation of most of the TB suspicions that could remain unconfirmed at the time of database lock.

Table 4 Censoring rules for triggered primary analysis when all subjects have completed 24 months of follow-up

Scenario	Sub-scenario	End date and censoring
Subjects with a suspicion of TB before the data lock point** but unconfirmed by laboratory results	Laboratory results confirmed positively before database freeze	End date = date when suspicion of TB is identified Case = yes → not censored
Subjects with a suspicion of TB before the data lock point** but unconfirmed by laboratory results	Laboratory results confirmed negatively before database freeze	End date = data lock point** Case = no → censored
Subjects with a suspicion of TB before the data lock point** but unconfirmed by laboratory results	Laboratory results not confirmed before database freeze *	End date = date when suspicion of TB is identified Case = no → censored
Subjects with a suspicion of TB before the data lock point** and confirmed positively by laboratory results before the data lock point**		End date = date when suspicion of TB is identified Case = yes → not censored
Cases when suspicion of TB is identified with a date after the data lock point**.		End date = data lock point** Case = no → censored
Subjects having finished the study (month 36) before the data lock point** without being a case		End date = date of month 36 visit Case = no → censored
Subjects dropping-out before the data lock point** without being a case		End date = last contact date Case = no → censored
Subjects still on study and not yet a case by the time of the data lock point**.		End date = data lock point** Case = no → censored

*Should be with very small frequency due to the lapse of time (6 weeks) considered between database lock point and database freeze

**Data lock point = last subject M24 visit date

Note: In this table, only lab confirmation or not of the TB suspicion is considered, but there are other elements involved in the case definitions, elements which differ from case definition to case definition (ex: HIV status at time of TB diagnosis or timing of sputum sample with respect to TB treatment start). Therefor the censoring occurs for the non-cases at the date when last subject month 24 visit is completed (database lock point), or Month 36 visit or last contact date or date of suspicion if lab data is pending or date of positive lab result if not satisfying the considered case definition whichever comes first.

10.3. End of Study analysis (EOS)

For the analysis at the end of the study: for non-cases, the end date is the date of the last contact for drop-out or the date of the Month 36 visit for subjects who went up to the end of the study. The time is then considered as censored.

For the analysis at the end of the study, for the cases, the end date is the date when suspicion of TB was identified for TB cases 1 to 6.

Table 5 Censoring rules for EOS analysis

Scenario	End date and censoring
Cases	End date = date when suspicion of TB is identified Case = yes → not censored
Subjects having finished the study (Month 36) without being a case	End date = date of Month 36 visit Case = no → censored
Subjects dropping-out without being a case	End date = last contact date Case = no → censored

11. STATISTICAL METHODS

11.1. Overview of recruitment

A line plot of subject accrual by study centre for all subjects in the TVC population as of date of data cut-off will be presented. Time elapsed from study start will be presented on the x-axis; the cumulative number of subjects vaccinated at each time from start will be presented on the y-axis. The figure will plot subject accrual by study centre (e.g., using separate lines representing study centres) and total.

11.2. Demography, study cohorts and baseline characteristics

11.2.1. Study cohorts

The reasons why screened subjects are not enrolled will be displayed by treatment group.

The number of subjects who attended each study visit and the identification numbers of subjects who withdrew from the study along with the reason for withdrawal will be displayed per treatment group. As this gives a list of identification numbers per group, this will only be produced for the EOS analysis.

Reasons for drop-out from the study will also be summarised by vaccine group for both the triggered primary analysis when all subjects have completed their Month 24 visit and for the end of study analysis.

The age at the first vaccination and the intervals between visits defined in the protocol should be followed as closely as possible. Subjects falling outside of these intervals will be reviewed and excluded from the ATP immunogenicity analysis (code 2xxx) if they don't respect the maximum interval allowed and excluded from the ATP efficacy analysis for the interval between the 2 doses of the TB vaccine or placebo (code 3xxx):

Table 6 Intervals between study visits

Interval	Size of interval per protocol*	Maximum interval allowed	Elimination code
Visit 1 (screening) → Visit 2 (Day 0)	0-30 days	0 to 30 days	No elimination code
Visit 2 (Day 0) → Visit 4 (Day 30)	26-35 days	26 to 50 days**	code 2080 and 3080
Visit 4 (Day 30) → Visit 6 (Day 60)	26-35 days	26 to 50 days**	code 2090
Visit 4 (Day 30) → Visit 7 (Month 12)	10 months -12 months	285 days- 380 days **	code 2090
Visit 4 (Day 30) → Visit 8 (Month 24)	22 months -24 months	645 days- 745 days **	code 2090
Visit 4 (Day 30) → Visit 9 (Month 36)	34 months -36 months	1005 days- 1110 days **	code 2090
Visit n → next contact	6 weeks -12 weeks	42 days- 84 days	No elimination code
Contact n → Contact n+1	6 weeks -12 weeks	42 days- 84 days	No elimination code

*Subjects may be eligible for inclusion in the ATP cohort for analysis if they make the study visit outside this interval.

** Subjects will not be eligible for inclusion in the ATP cohort for immunogenicity (code 2xxx) or efficacy (code 3xxx) analysis if they make the study visit outside this interval.

Table 7 Intervals between study visits specific for the safety and immunogenicity sub-cohort

Interval	Size of interval per protocol	Elimination code
Visit 2 (Day 0) - Visit 3 (Day 7)	6 days - 10 days	No elimination code
Visit 4 (Day 30)- Visit 5 (Day 37)	6 days - 10 days	No elimination code

The number and percentage of subjects included in each of the study cohorts as well as the reason(s) for elimination will be presented per treatment group: One table for subjects of the safety and immunogenicity sub-cohort to indicate those subjects who are eliminated from safety and/or immunogenicity analyses and one table for all the subjects to indicate those who are eliminated from safety and/or efficacy analyses.

For each activity, the minimum and maximum dates over all vaccinated subjects will be presented per treatment group.

Enrolment in each study site will be tabulated by group.

11.2.2. Demography and baseline characteristics

All the analyses in this section will be presented by treatment group, and also by study centres and treatment group and by country and treatment group.

Demography and baseline characteristics will be displayed in one table for all subjects in the TVC, in TVC for efficacy, in the ATP for efficacy and in the ATP for immunogenicity.

Categorical variables will be presented by percentages and numerical variables will be summarized by mean, standard deviation, minimum, Q1, median, Q3, and maximum. For the age, minimum and maximum will not be presented.

Demographic parameters (age at first vaccination, gender and race) will be presented by treatment group. The Body Mass Index (BMI) at baseline will be summarized by mean, standard deviation, minimum, Q1, median, Q3 and maximum by group for all subjects.

The percentage of subjects recently exposed (within the last 12 months) to a household contact diagnosed with and/or treated for pulmonary TB disease will be presented by treatment group.

The percentage of subjects diagnosed with diabetes at screening will be presented by treatment group.

The percentage of subjects diagnosed with a chronic pulmonary condition such as asthma, COPD at screening will be presented by treatment group.

The percentage of subjects with each of the 4 smoking histories will be presented by treatment group.

A variable indicating whether a subject was vaccinated with BCG and/or has a BCG scar (yes to one of the 2 questions) will be derived and summarized by treatment group.

11.3. Evaluation of study population during the study period

The Body Mass Index (BMI) will be summarized by mean, standard deviation, minimum, Q1, median, Q3 and maximum by group and at each timepoint when weight is measured (at baseline Day 0, at Month 12, at Month 24 and at Month 36). For the subjects who were identified as a case (whatever the definition), BMI and weight will be tabulated at baseline and at the time they meet any case definition.

The follow-up time will be summarized by mean, standard deviation, minimum, Q1, median, Q3 and maximum, by group.

All the enrolled subjects are HIV negative at entry due to the inclusion/exclusion criteria, the percentage of subjects becoming positive in each treatment group will be presented.

In case of positive HIV results, the CD4 count is measured. For those subjects, the descriptive statistics (N, mean, standard deviation, min, Q1, median, Q3, max) will be displayed by group.

11.4. Efficacy

11.4.1. Analysis

VE will be estimated from a Cox proportional hazard regression model (VE=1-hazard ratio) and 90% CIs and Wald p-value will be derived. The primary analysis will be unadjusted but secondary analyses will evaluate the effect of potential covariates.

At the case-driven analysis of efficacy (primary analysis), the success criterion for the primary objective is the following:

The LL of the 90% two-sided CI for the VE (using a Cox regression model) against first occurrence of Definite pulmonary TB disease not associated with HIV-infection, meeting the first case definition, is above 0%.

Kaplan-Meier survival curves for the vaccine and control groups will be presented together with p-values from the logrank test.

If the primary objective is met, the confirmatory secondary objective will be evaluated with the following success criterion:

The LL of the 90% two-sided CI for the VE (using a Cox regression model) against first occurrence of Definite pulmonary TB disease not associated with HIV-infection, meeting the second case definition, is above 0%.

For all other secondary efficacy objectives, Kaplan-Meier survival curves will be plotted and compared by means of the logrank test. The magnitude of the vaccine efficacy will be estimated using Cox regression.

For the primary case definition, the number and proportion of cases will be given by vaccine group and by the number of doses received (1 or 2).

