11.4.2. Treatment of ties

In case of ties (i.e. more than one case at the same time, very unlikely with such a small incidence), the Breslow method will be used.

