11.4.3. Covariates

The Cox regression methodology can take into account specific risk factors which might have been imbalanced, by chance, at the beginning of the trial between the vaccinated and control group.

As a secondary analysis, ATP analyses evaluating first or only episodes of first case definition will also be performed adjusting for other covariates. Covariates are:

- Country
- Gender
- Diabetes at screening
- Year of occurrence (time-dependent covariable, treated differently)
- Age: $\leq 25, > 25$
- The variable indicating whether a subject was vaccinated with BCG and/or has a BCG scar
- Smoking: currently smoker or not

Please find in the below table how the variable indicating whether a subject was vaccinated with BCG and/or has a BCG scar is defined based on data coming from the CRF

CRF categories for BCG history (previous BCG vaccination)	CRF categories for presence of a BCG vaccination scar	The covariate= subject was vaccinated with BCG and/or has a BCG scar
Yes	Yes	Yes
Yes	No	Yes
Yes	Not done	Yes
No	Yes	Yes
No	No	No
No	Not done	Unknown
Unknown	Yes	Yes
Unknown	No	Unknown
Unknown	Not done	Unknown

Please find in the below table how the current smoker is defined based on data coming from the CRF

Categories for smoking history in the CRF	Current smoker
Yes, currently smoking cigarettes every day	Yes
Yes, currently smoking cigarettes some days	Yes
No, currently not but previously regularly	No
No, currently not but never regularly	No

The VE will be given at each level of each of these covariates, like for a subgroup analysis. A forest plot will be given representing these VE and their 90% CI. This is really exploratory and requires caution in interpretation due to the low number of cases.

Due to the low number of cases, the decision to adjust for all the covariates all together or in a univariate way will be taken based on the outcome of the model fit (if standard deviation is too high, or coefficient is infinity or the model did not converge, then the adjustment will be univariate, covariate by covariate separately, [Harrell1984], [Harrell1996], [Peduzzi1996] Subjects with missing values for the covariates taken into account into the model will be not considered into the model.

For the year of occurrence, as it is a time-dependent covariate, this will be analysed through the piecewise Cox model.

```
proc phreg data=TB OUTEST=oo COVOUT;;
model fu_year*event(0)=treatt1 treatt2;
treatt1 = GROUP * (fu_year LE 1.5);

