11.7. Assessment of cases versus baseline characteristics

The descriptive statistics (N, mean, standard deviation, min, Q1, median, Q3, max) of the age of the cases will be displayed without split by group for the triggered primary analysis but by group for the end of study analysis.

The distribution of the cases (n) will be given according to gender and according to country without any split by vaccine group for the triggered primary analysis but by group for the end of study analysis.

11.8. Sensitivity analysis for the case definition 1

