The bilirubin grading scale at a given time-point will depend on the liver function tests (ALT and AST) at the corresponding time-point. When both liver function tests are normal, i.e. when ALT and AST are grade 0 according to the FDA grading (reference: *FDA Guidance for Industry: Toxicity Grading Scale for Healthy Adult and Adolescent Volunteers Enrolled in Preventive Vaccine Clinical Trials (September 2007)*), the “Bilirubin – when Liver Function Test is normal” scale will be applied while when at least one of the liver function tests (ALT or AST) is grade 1 or above, the “Bilirubin – when accompanied by any increase in Liver Function Test” scale will be applied. In the descriptive analysis, the bilirubin grades will be presented together regardless of the scale used.

Vitamin D is measured at screening in all subjects of the immuno and safety sub-cohort. Levels will be summarized by mean, standard deviation, minimum, Q1, median, Q3 and maximum by group at baseline inside the safety and immunogenicity sub-cohort.

The number and percentage of subjects with vitamin D deficiency in the immune and safety sub-cohort will be tabulated where Vitamin D deficiency is defined as serum 25(OH) D concentrations : < 20 ng/mL.

One laboratory parameter is analysed independently of the sub-cohort:

HbA1C is measured in confirmed TB cases. For those subjects, the descriptive statistics (N, mean, standard deviation, min, Q1, median, Q3, max) will be displayed by group.

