13.2. Blinding

The study is ‘double-blinded’ meaning that the vaccine recipient as well as those responsible for the evaluation of study endpoint data are unaware which treatment, M72/AS01_E or control vaccine, was administered to a particular subject. It also means that data monitors and GSK and AERAS central staff are blinded to treatment allocation and the database kept at GSK does not contain information that can lead towards un-blinding individual trial subjects (randomization list, immunogenicity data). As the primary objective, can be analysed before trial end, specific procedures are in place to continue the trial in a blinded way. The data cleaning is performed in a blinded way and the data analysis will be performed by statisticians external to the GSK-AERAS clinical teams and the investigator groups. Moreover, analysis outputs will be checked and blinded wherever applicable for GSK and AERAS (In the tables, the external statistician will, in case of a distribution of 15 vs 0 for an unsolicited AE, put 15 in each of the 2 columns with a double star to indicate that here one of the 2 groups has 15 subjects and 0 the other, not letting us know in which group.) and no individual subjects data will be generated and distributed before formal un-blinding of the trial. No individual listings, no identification numbers by group (for example for the drop-out tables) will be produced at the triggered primary analysis when all subjects have completed their Month 24 visit. Those will only be produced for the end of study analysis.

For the IDMC, the analysis output will be fully unblinded (no double star).

If required in order to fully grasp the risk/benefit of the vaccine during the review of the primary results, specific table(s) or even specific row(s) will be unblinded after discussion, agreement and documentation. We expect blinding stars to appear in few tables, mainly for events with very small incidence.

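### The SAP keeps the sponsor team blinded to Month 36, but its unrestricted Month 24 Kaplan-Meier curves and by-group HbA1c in TB cases could reveal the arm of many existing cases

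*SAP*

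**What the plan says.** The trial has one epoch, double-blind to Month 36 (Protocol 3). SAP 13.2 has external statisticians run the Month 24 analysis and keeps central staff of the sponsor and its partner blinded. Outputs are checked and masked for them where applicable, and "no individual subjects data will be generated and distributed before formal un-blinding of the trial".

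Three specific rules follow:

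- 13.2.1 masks demographic categories found in one arm only.
- 13.2.2 does the same for adverse events.
- 13.2.3 masks covariate levels where all events fall in one arm, plus one further level.

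Some by-arm case outputs are held back. SAP 11.5 gives the Xpert-by-culture table within arms only at end of study. SAP 11.7 gives cases by gender and country "without any split by vaccine group for the triggered primary analysis but by group for the end of study analysis", and treats age the same way.

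Two other outputs carry no such limit. SAP 11.4.1 states that "Kaplan-Meier survival curves for the vaccine and control groups will be presented together with p-values from the logrank test", and adds: "For all other secondary efficacy objectives, Kaplan-Meier survival curves will be plotted and compared by means of the logrank test". SAP 11.17 notes that "HbA1C is measured in confirmed TB cases" and shows the results by group with N, mean, SD, minimum, quartiles and maximum.

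**The concern.** With so few cases, a Kaplan-Meier curve by arm is close to a listing of event times by arm. The people meant to stay blinded already know the cases individually: cleaning is done blinded (SAP 13.2), and cases are reviewed every two months, then weekly from 18 cases (SAP 9). SAP 11.8.1 and 14 show the team discussing how many cases rested on a single positive test.

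If a step can be matched to a known case, that case's arm is known a year before unblinding. The Clinical Research and Development Lead may still be judging whether a medication or condition justifies elimination from the ATP cohort (SAP 6.4), and the Month 36 efficacy analysis uses that cohort. Nothing in the SAP says that case status and elimination codes settled for Month 24 stay fixed.

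**Working it through.** **1. How many steps.** Protocol 11.3 gives 80% power, hazard ratio 0.30 and two-sided 10% significance. Freedman's formula reproduces its figure:

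events = (1.645 + 0.842)² × (1.3/0.7)² = 6.183 × 3.449 = 21.3, stated as 21.

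The expected split uses 1,753 per arm, 0.55% a year, 2 years and 15% loss: control 1,753 × 0.85 × 0.011 = 16.4; vaccine 16.4 × 0.30 = 4.9. So about 16 and 5. The SAP now waits for every Month 24 visit rather than for 21 cases, so more are possible; 40 is shown as well.

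**2. What a step shows.** In SAP 10.1 the time is end date minus origin plus 1, with the origin 30 days after dose 2 (ATP) or at Day 0 (TVC). In SAP 10.2, Table 4, a case's end date is the day suspicion was identified. Dose and suspicion dates are in the data being cleaned blinded. SAP 11.4.2 calls ties "very unlikely with such a small incidence", so a step is normally one person.

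**3. How often a step fixes the arm.** Count a case as placed if no case of the other arm lies within the read-off error ±r days. With case times even over T days and p = (2r + 1)/T, the expected share for 5 v 16 is approximately

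[16(1 − p)⁵ + 5(1 − p)¹⁶] / 21.

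For r = 14 and T = 690: p = 29/690 = 0.0420, giving (16 × 0.807 + 5 × 0.503)/21 = 0.734. Simulation (4,000 runs per setting) gave 0.737. Simulated shares in per cent, for T = 690 to 1,035:

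| Read-off error | 5 v 16 | 8 v 13 | 10 v 30 | 13 v 27 |
|---|---|---|---|---|
| ±1 day | 96.7–97.8 | 95.7–97.2 | 93.7–95.8 | 92.7–95.1 |
| ±7 days | 85.1–89.6 | 80.5–86.5 | 73.2–81.0 | 68.7–78.1 |
| ±14 days | 73.7–81.4 | 65.9–75.7 | 56.0–67.4 | 49.3–61.9 |

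Two cautions apply. Every case is placed less often: for 5 v 16, in 70 to 79% of runs at ±1 day and 18 to 31% at ±7 days. And calling every case a control would already be right for 16/21 = 76%; what the curve adds is near-certainty for particular cases. The smaller arm is the harder to place: in the worked example, 50% of vaccine cases against 81% of control cases. These figures use one curve. The ATP and TVC curves have different origins and several case definitions are plotted, so reading them together can only help.

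**4. HbA1c.** With five cases in an arm, minimum, Q1, median, Q3 and maximum are the five individual values under the SAS default quantile definition (assumed; the SAP names none). With seven, they are five of the seven. HbA1c covers all confirmed TB cases, so an arm may hold more; the minimum and maximum remain individual values.

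**5. Do the masking rules trigger?** The rules in 13.2.1 and 13.2.2 concern demography and adverse events found in one arm only. The rule in 13.2.3 concerns covariate levels. None applies to a survival curve or to HbA1c with cases in both arms.

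**The case against.** The strongest reply is that SAP 13.2 already requires all output to be checked and masked where applicable, and that figure formats sit in a separate table and figure list not available here. The external statistician might therefore coarsen the curves unprompted. That is possible, but the written rules are triggered by n-versus-0 patterns, and nothing tells the statistician that curves count. Where the authors saw a risk in 11.5 and 11.7, they wrote it down.

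By-arm curves are also specified in Protocol 11.7, and SAP 13.2 allows documented unblinding of particular tables or rows for a benefit-risk review. So withholding curves altogether would be a debatable trade-off; coarsening them is not.

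Reading accuracy matters too. On an assumed 15 cm axis, 690 to 1,035 days is 4.6 to 6.9 days per mm, so ±1 day is optimistic for a printed figure. The ±7 and ±14 day rows are the fairer test, and most cases are still placed there at the planned number.

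A reader might infer more than the documents support:

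- **VE by covariate level.** "The VE will be given at each level of each of these covariates, like for a subgroup analysis" yields at most an aggregate split within a level. It identifies individuals only when all events are in one arm, which 13.2.3 masks.
- **CD4 by group.** It is measured in HIV-positive subjects; case definitions 1 to 3 require HIV-negative status.
- **BMI in cases.** SAP 11.3 does not say it is split by group.
- **Case status decided again at Month 36.** No section says that Month 24 cases are adjudicated anew. Definitions 1 to 4 rest on laboratory results from a blinded laboratory (Protocol 6.3), definition 5 on the site investigator, and 13.2 does not describe release of outputs to sites.

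**Conclusion.** The point holds as a gap between the blinding that SAP 13.2 states and two outputs that no specific rule covers. At about 5 v 16 cases, roughly 97% could be placed in an arm at ±1 day and 74 to 81% at ±14 days. With 40 cases the ±14 day range is 49 to 67%. These figures assume evenly spread case times, a 690 to 1,035 day window, the stated splits, and a sponsor figure drawn as ordinary steps.

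It would be wrong to conclude that the primary result is at risk. Data are frozen before the Month 24 analysis (SAP 10.2), all alpha is spent there (SAP 13.3), and only people who are already cases are exposed. Non-cases, who supply the events after Month 24, stay blinded. The exposure is to blinded conduct in the last year, including discretionary eliminations, and to the Month 36 efficacy analysis, which is descriptive. That makes it a cheap correction worth making before the Month 24 output is released.

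**What to change.** Extend SAP 13.2.3 to the sponsor's version of the Month 24 output:

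- Pool HbA1c in TB cases over arms.
- Replace step curves by cumulative incidence with CI and numbers at risk on a time grid fixed in advance, for example every 6 months. Apply the SAP's own n-versus-0 idea to the grid: merge an interval with its neighbour if all its cases are in one arm. This will often be needed. With 5 vaccine cases spread evenly over four intervals, the chance that every interval has at least one is 240/1,024 = 23%.
- Give full curves and by-group HbA1c to the IDMC, which already sees unmasked output, and to the end-of-study report.

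Also state that case status and ATP elimination codes for events up to the Month 24 lock are frozen, and may change later only on documented new source data.

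The cost is SAP wording and a little programming by the external statistician. The sponsor sees a coarser curve until Month 36, but still receives the VE estimate, its CI and the p-values.
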